Layered stigma is associated with worse outcomes than HIV stigma alone. Stigma is best understood as a dynamic social process rather than an individual attribute.^{27,28} When stigma is layered, social devaluation from two socially discrediting conditions can operate synergistically. Households undergoing TB contact investigation face or anticipate facing at least two stigmatized conditions, HIV and TB. TB-HIV stigma has consequences for TB care-seeking, TB-HIV outcomes, and HIV management.²⁹

Uganda provides a representative setting for expanding and improving home HIV testing by reducing household stigma for HIV & TB. Uganda is a high HIV-TB-burden country, with estimated HIV prevalence of 7.1% and TB prevalence of 253 per 100,000. More than 25% of PLWH are unaware of their HIV status.³⁰ Uptake of door-to-door home HIV testing ranges from 69%–95%^{7,8,13}, but uptake of HIV testing among household contacts of TB patients is only 53%.²⁰ The PLWH Stigma Index found that >60% of Ugandan PLWH experienced malicious gossip in their family or community in the past year and nearly 10% had been excluded from family activities.³¹ TB stigma may be even more common in Uganda; nearly 50% of survey respondents hold stigmatizing attitudes toward TB, compared to 26% with stigmatizing attitudes toward HIV.³²

There is a need to build awareness of and capacity for integrating stigma hypotheses and measures into research on HIV-TB in Uganda. We propose two specific capacity-building initiatives that will draw on experiences building capacity for mixed-methods and implementation research through our Fogarty D43 Pulmonary Complications of AIDS Research Training program. First, we will sponsor a doctoral student from Makerere University to work on this project. Second, each year, we will sponsor a symposium highlighting current research and future priorities in HIV and TB stigma at the Makerere Joint Annual Science and Health Conference at Makerere University, and include patients, families, researchers, and program officials.

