TB and HIV stigma scales Study CHWs will individually administer the short-form HIV-TB stigma scales to all study participants regardless of group using the CommCare application alongside a visual aid. These scales have a total of 13 items and were validated in the Uganda setting as part of the Aim 1 procedures. The scales will be administered first at the beginning of the home visit, then again at its conclusion. Each time, the CHW will briefly orient the participant to the response categories using a visual aid.

Documentation and Data management All enrollment procedures, household contact interviews and HIV testing details will be collected using CommCare. All forms will be available within a customized CommCare application that prevents common errors (such as not filling out a question etc.). Quality control procedures will include review of all study data collection forms for completeness and accuracy, including quality assurance testing of all validation and skip logic within the application, prior to study initiation. The US study coordinator will initiate reports on missing data and provide feedback to all study team members on the quality of quantitative data. All changes will be recorded using a data management google doc tracking sheet that contains information on the change, who made the change and a link directly to the location of the change on CommCare. Any duplicate cases (i.e. two cases for one index patient or contact) will be archived and similarly recorded.

Follow-up interview. At 3 months, the study LHW or a member of study team will contact a subset of households to schedule a follow-up visit or phone call if a second visit is unable to occur. The study LHW or a member of the study team will re-administer stigma scales to each participating member. Household members who are not present at the second household visit will be contacted by telephone to schedule a follow-up interview.

Sample Size.

During aim 2, we will distribute the stigma scales up to approximately 152 households containing approximately 304 household contacts with approximately 1:1 randomization (half in each study arm). We analyzed power for a 2-arm household-randomized, controlled trial using mixed models tests for two proportions in a two-level hierarchical design (household, contact). The assumptions and parameters within these calculations were based on data from Aim 1 and include:

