- Has an index patient with confirmed TB via clinical diagnosis

Exclusion:

- Fewer than 2 household contacts over age 14
- Lives outside of greater Kampala area

Contacts: We will include all adult household contacts of TB patients.

Inclusion:

- Household contact to a TB patient
- ≥ 15 years of age

9. How will **eligibility** be determined, and by whom? Write here

Eligibility of households and individual clients will be determined according to answers to routine screening questions used during household contact investigation by the lay health worker carrying out household contact investigation. If the individual is eligible, the lay health worker will invite them to the study.

For interviews with health care workers, individuals will be identified by the study team based on the employment records at the health centres of interest in Kampala, Uganda.

10. **Risks:** Describe the reasonably foreseeable risks, including risks to subject privacy, discomforts, or inconveniences associated with subjects participating in the research.

There are minimal risks to participants in this study. The primary risks to both index TB patients and to their household contacts are the psychological and social risks of disclosure of private information such as place of residence, or of disclosure of an individual's TB diagnosis and/or HIV status. The primary research risks for health-care workers arising from the qualitative studies are the potentially punitive actions by the employer in response to the information they provide for research.

11. **Minimizing Risks:** Describe the manner in which the above-mentioned risks will be minimized.

As is done in routine practice, lay health workers will make every effort to preserve the privacy and confidentiality of individual participants during household contact investigation. While individuals who have decided to test may be invited to voluntarily share their decision to test with their peers, individual testing and counseling will be carried out privately. Results will be delivered in private and contacts will not be asked to disclose their status following the test. Disclosure of participant HIV or TB status is expected to be rare, if it occurs. No other adverse effects are expected.

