This protocol presents minimal risks to the subjects and Unanticipated Problems Involving Risks to Subjects or Others (UPIRSOs), including adverse events, are not anticipated. In the unlikely event that such events occur, Reportable Events (which are events that are serious or life-threatening and unanticipated (or anticipated but occurring with a greater frequency than expected) and possibly, probably, or definitely related) or Unanticipated Problems Involving Risks to Subjects or Others that may require a temporary or permanent interruption of study activities will be reported immediately (if possible), followed by a written report within 5 calendar days of the Principal Investigator becoming aware of the event to the IRB (using the appropriate forms from the website) and any appropriate funding and regulatory agencies.

The investigator will apprise fellow investigators and study personnel of all UPIRSOs and adverse events that occur during the conduct of this research project through 1) weekly study meetings carried out via teleconference during and immediately following the data collection period, or 2) via email as they are reviewed by the principal investigator. The protocol's research monitor(s), Fogarty International Center of NIH (sponsor/funder) and the relevant IRB of Makerere University (local collaborator/host) will be informed of any UPIRSO, including adverse events, or Reportable Event within 5 days of the event becoming known to the principal investigator.

13. Statistical Considerations: Describe the statistical analyses that support the study design.

Aim 1 is a formative qualitative study to refine an intervention; it is not designed for statistical tests. Based on the findings of the formative study described here, the study team will specify the final intervention and submit a modification to this protocol for a pilot study evaluating that intervention.

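### No described Aim 2 contact asks about disclosure or social harm, so the quarterly safety review rests on passive reports and would probably under-count the risk the protocol names as primary

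*Combined protocol and SAP*

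**What the plan says.** All references are to Section I of the combined protocol and SAP.

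- **Named risk.** Item 10 (Risks): "The primary risks to both index TB patients and to their household contacts are the psychological and social risks of disclosure of private information". The sentence goes on to include a person's TB diagnosis and HIV status.
- **Expectation.** Item 11 (Minimizing Risks): "Disclosure of participant HIV or TB status is expected to be rare, if it occurs. No other adverse effects are expected". Disclosure is thus an anticipated adverse effect, and the only one. Its expected frequency has no number.
- **Reporting to the IRB and agencies.** Item 12 (Data and Safety Monitoring Plan) covers "Reportable Events (which are events that are serious or life-threatening and unanticipated (or anticipated but occurring with a greater frequency than expected", and at least possibly related. It adds a second category: "Unanticipated Problems Involving Risks to Subjects or Others that may require a temporary or permanent interruption of study activities will be reported immediately".
- **Other routes in item 12.** Internally, "The investigator will apprise fellow investigators and study personnel of all UPIRSOs and adverse events that occur during the conduct of this research project". The research monitor, the funder and the host-country IRB are to hear within 5 days of any UPIRSO (unanticipated problem involving risks to subjects or others), adverse events included, or any Reportable Event.
- **Safety review.** Item 12 has the principal investigator review safety quarterly and decide whether to continue, modify or close. The review is not restricted to Reportable Events.
- **Scheduled data collection.** Item 4 (Research Plan) gives the 13-item stigma scales at the start and end of the home visit. At 3 months a subset of households is contacted, and the study team "will re-administer stigma scales to each participating member". The size of the subset and how it is chosen are not stated.

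**The concern.** The risk that the protocol puts first has no planned measurement. The stigma scales include a disclosure domain, but it concerns attitudes to disclosing disease. It does not record whether someone's status or test decision became known against their wishes.

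This matters more here than in a routine testing programme. Intervention households receive opt-out framing, a message that presents testing as setting an example for the household, and an invitation to the first tester to tell the others that they tested. The protocol itself treats the test decision as sensitive: people who decline are given a survey of similar length to testing so that others cannot tell. Pressure to test, unwanted disclosure and household conflict are the harms that this package could plausibly shift.

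At stake is what the quarterly decision and the later randomized study can learn. If events reach the team only when someone volunteers them or a health worker notices, few events may mean few harms or few reports. Capture may also differ by arm, because the two arms are served by different health-worker teams.

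**Working it through.** **Step 1. Apply the reporting text to one ordinary event.** Suppose that a contact's positive result becomes known in the household, with distress but no grave consequence.

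| Route (item 12) | Test | Does the event meet it? |
|---|---|---|
| Reportable Event | Serious or life-threatening | Usually not |
| | Unanticipated, or above expected frequency | Anticipated (items 10 and 11); the frequency test is a judgement, since rare has no number |
| UPIRSO to IRB and agencies | Unanticipated and may interrupt the study | Unlikely for one event |
| Monitor, funder, host IRB | Any UPIRSO, including adverse events | Unclear: wider wording, but still attached to unanticipated problems |
| Study personnel | All UPIRSOs and adverse events | Yes, if the event becomes known |

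Item 12 also says that adverse events are not anticipated, whereas item 11 anticipates one. A health worker could not tell from this text to whom the event goes.

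**Step 2. Look for a contact that asks.**
- End of visit: stigma scales, given before most consequences could arise.
- 1 month: linkage to HIV care among new positives.
- Clinic follow-up: recorded by the clinic-based team; no harm question described.
- 3 months: stigma scales, undefined subset.
- Later interviews or surveys: optional, on implementation and impact.

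None is described as asking about disclosure, pressure, conflict or exclusion.

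**Step 3. Illustrate passive capture.** The plan has no figure to reproduce. Inputs from the plan: 152 index patients + 304 contacts = 456 people. The event rate r and the share c that surfaces unprompted are assumptions.

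Expected events seen = N × r × c. P(at least one seen) = 1 − (1 − r × c)^N.

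| r (N = 456) | Events | c = 0 | c = 10% | c = 25% | c = 50% |
|---|---|---|---|---|---|
| 0.5% | 2.3 | 0% | 20% | 44% | 68% |
| 1% | 4.6 | 0% | 37% | 68% | 90% |
| 2% | 9.1 | 0% | 60% | 90% | 99% |

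At r = 1% and c = 10%, 456 × 0.01 × 0.10 = 0.46 events are seen out of 4.56. For the 304 contacts alone at r = 1%, the chances are 26%, 53% and 78% at c = 10%, 25% and 50%.

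**Step 4. What a record of zero events would show.** There are about 304 / 2 = 152 contacts per arm. With zero events the one-sided 95% upper bound is 1 − 0.05^(1/n).

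- All 152 asked, full reporting assumed: 1 − 0.05^(1/152) = 1.95%. If harms clustered like test uptake (ICC 0.59, 2 contacts per household, assumed), the design effect is 1 + 0.59 = 1.59, the effective n is 152 / 1.59 = 95.6, and the bound is about 3.1%.
- Only a 25% subset asked (38 contacts, assumed): 1 − 0.05^(1/38) = 7.6%, or about 11.8% with the same clustering.
- Nobody asked: the 1.95% bounds r × c, not r. At c = 10% the bound on r is 1.95% / 0.10 = 19.5%; at c = 50% it is 3.9%. With c unknown there is no usable bound.

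**The case against.** Three stronger readings are tempting, and the documents do not support them.

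- *The definition shuts disclosure out.* It does not. A serious, related disclosure occurring more often than expected qualifies, and one of an unanticipated kind or severity could qualify as a Reportable Event or UPIRSO. The missing number for rare leaves that test to judgement; it does not make it unusable.
- *The quarterly review would see nothing whatever happens.* This needs passive capture to be exactly zero, which the documents do not say. All known adverse events go to study personnel with no seriousness threshold, and the review is not limited to Reportable Events. It also covers protocol compliance, so a health worker who revealed a result, which the referral protocol forbids, would be within its remit. Linkage follow-up, clinic records and the phone number given to people who test positive are further channels.
- *The Background's stigma figures give a count of missed harms.* That section reports the share of Ugandan people with HIV who "experienced malicious gossip in their family or community in the past year and nearly 10% had been excluded from family activities". This is background experience, part of it in the wider community, and much of it would occur without the study.

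It is also fair that the minimal-risk rating is a prospective judgement for the ethics committee, that comparing harms between arms is not a stated objective, and that 5-day reporting of every non-serious event would be a policy choice. Finally, the data-collection forms and information sheets are not in the supplied text, so a harm question or complaint route may exist there.

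What remains is the gap in ascertainment. The channels listed could let a harm surface, but none is described as asking about it, and the item 12 thresholds still disagree.

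**Conclusion.** The concern holds as one of probable under-counting and unclear reporting. On the text supplied, the review of the protocol's primary risk depends on events being volunteered or noticed, and most single disclosures would not qualify as Reportable Events.

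The size cannot be fixed from the documents. At an assumed 1% event rate, the chance of seeing even one event among 456 people runs from 37% at 10% capture to 90% at 50% capture. A clean record under unknown capture therefore says little, whereas zero events after asking every intervention contact would bound the rate at about 2% to 3%. That bound assumes honest answers and covers only events that have occurred by the time of asking. The Step 3 figures ignore clustering within households.

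This is worth correcting because it is cheap and bears on participant safety. It does not show that harm is occurring, and it does not affect the validity of the stigma or uptake comparisons.

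**What to change.** 1. **Ask.** Add three or four private yes/no items for all contacts in both arms: unwanted disclosure of HIV or TB status or of the test decision, pressure to test, and conflict or exclusion linked to the visit. Place them after the second stigma scale so that they cannot influence the primary outcome. Repeat them at the 3-month contact; if only a subset of households is reached, draw it at random within arm.
2. **Review.** Tabulate these events by arm at each quarterly review, whatever their seriousness or expectedness.
3. **Reconcile.** Align items 10 and 11 with the two reporting paragraphs of item 12, so that it is clear that a study-related disclosure is recorded and who is told.

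If the existing forms already contain such items, the first step reduces to describing them in the protocol.

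The cost is a protocol amendment, a few extra questions in the data-capture application, about two minutes per contact, and some more recorded events. No extra staff are needed. A number for the expected frequency is not essential, and rapid reporting of every non-serious event can be left to the sponsor and the IRBs.

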After enrollment, CHWs will introduce themselves and ask for the introduction of contacts and it is at this time when a contacts master list will be created. Index patients will then be asked the influence questions. The questions will be asked in two steps, once to capture the number and once to capture the name. The other CHW will go head to conduct routine TB contact investigation activities.

b) Household contact screening interview

After household contact enrolment, each contact will undergo a short interview. This interview will capture age, gender, occupation (if applicable), income (if applicable), education in years, relationship to index patient, history of testing for HIV, month and year of last HIV test, and self-reported symptoms of TB (including cough, subjective fever, or weight loss).

The short (13-item) version of the Van Rie TB- and HIV-related stigma scales will be administered immediately prior to TB screening, as well as at the conclusion of the visit. We will ask the index patient to share the number of rooms in the dwelling, the number of windows in the dwelling, and the number of individuals (including children) who dwell there. All screening interview components will be conducted by a CHW. Screening interview components are identical for all study groups.

c) HIV testing procedures

Working in teams of two, CHWs will provide household contact investigation services, including offering oral HIV testing. One CHW will lead and accompany each HIV test while a colleague leads other household members through TB screening.

To begin, the CHW responsible for offering HIV testing will individually invite the client to a place apart from the others. S/he will detail the process of HIV testing in Luganda and/or English, per client preference. A pictorial guide may be used to help walk the client through each step of the process using a Luganda- or English-language guide. The CHW will then provide pre-test counselling.

Consenting household contacts who choose to test for HIV will swab their own gums. CHWs will be fully trained to provide HIV counselling and support throughout all testing procedures.

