Analysis. In the Aim 2 analysis, our primary outcome is change in perceived HIV-TB stigma after following the first household contact tracing visit; the secondary outcome is uptake of HIV testing; we will descriptively assess linkage to care from both baseline data and intervention households. We will calculate descriptive statistics for participant characteristics, and test associations between characteristics and perceived/attributed household stigma. To test the hypothesis that invitation scripts that apply acceptance-optimized sequencing of oral test offers and prosocial messaging can decrease HIV stigma within households, we will evaluate change in HIV-TB stigma using cluster-adjusted dependent t-tests and fitting multilevel models with clustered standard errors. To test the hypothesis that prosocial messaging and theory-informed sequencing of HIV test offers can increase test uptake, we will compare testing uptake among the intervention households and pre-implementation households using cluster-adjusted chi-squared tests of proportion and by fitting multilevel logistic regression models. All hypothesis tests will be carried out at alpha of 0.05, corrected for multiple tests as appropriate. We will report household ICC for stigma as well as test uptake.

5. Genetic Testing N/A

6. **Subject Population:** Provide a detailed description of the types of human subjects who will be recruited into this study.

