In the Aim 2 analysis, we will calculate and compare uptake across each of the trial arms using an intention-to-treat analysis. We will also consider a per protocol analysis and model adjusted for imbalances in baseline confounders as secondary analyses. To test the hypothesis that a norming intervention can increase test uptake, we will compare testing uptake among the intervention households and control households using cluster-adjusted chi-squared tests of proportion and by fitting mixed effects logistic regression models with two levels (household, contact.) To test the hypothesis that invitation scripts that apply acceptance-optimized sequencing of oral test offers and prosocial messaging can decrease HIV stigma within households, we will evaluate change in HIV-TB stigma using cluster-adjusted dependent t-tests and fitting multilevel models with clustered standard errors. We will conduct a causal mediation analysis to determine to what degree the effects of the intervention on stigma explain the improvement in test uptake using observed-variable structural equation modeling. All hypothesis tests will be carried out at alpha of 0.05, corrected for multiple tests as appropriate. We will report household ICC for stigma as well as test uptake and will consider a household ICC of >0.2 a sufficient level of clustering necessitating adjustment.

SECTION II: RESEARCH INVOLVING DRUGS, BIOLOGICS, RADIOTRACERS, PLACEBOS AND DEVICES

If this section (or one of its parts, A or B) is not applicable, check off N/A and delete the rest of the section.

A. RADIOTRACERS N/A

B. DRUGS/BIOLOGICS N/A

B. DEVICES N/A

SECTION III: RECRUITMENT/CONSENT AND ASSENT PROCEDURES**1. Targeted Enrollment: Give the number of subjects:**

- a. Targeted for enrollment at Yale for this protocol: 0
- b. If this is a multi-site study, give the total number of subjects targeted across all sites:
 - 40 to 60 individuals drawn from 20 households (Aim 1)
 - Approximately 8 to 15 lay health workers with experience carrying out TB contact investigation
 - Approximately 60-100 health workers participating in HIV and TB care services during the COVID-19 pandemic
 - Approximately 152 index patients and their approximately 304 household contacts (Aim 2)

2. Indicate recruitment methods below. Attach copies of any recruitment materials that will be used.

 Flyers	 Internet/web postings	 Radio

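### The optional adjusted model chooses covariates by observed baseline imbalance, and the stigma analysis states no adjustment for the baseline score: name the covariates in advance

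*Combined protocol and SAP*

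**What the plan says.** Section I.13 sets an intention-to-treat comparison of uptake across arms as the main uptake analysis. The next sentence adds, as possibilities, a per-protocol analysis and a "model adjusted for imbalances in baseline confounders as secondary analyses". This is the only adjustment rule in the document. The uptake tests that follow, a clustered chi-squared test and a two-level mixed logistic model, name no covariates.

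For stigma, the Aim 2 Analysis paragraph of Section I.4 states that "our primary outcome is change in perceived HIV-TB stigma after following the first household contact tracing visit", and Section I.13 adds that "we will evaluate change in HIV-TB stigma using cluster-adjusted dependent t-tests and fitting multilevel models with clustered standard errors". No baseline term is mentioned.

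Useful baseline variables are collected on every contact. Under Household contact screening interview, the short stigma scales "will be administered immediately prior to TB screening, as well as at the conclusion of the visit". The same interview records age, gender, education and "relationship to index patient, history of testing for HIV, month and year of last HIV test". The Randomization paragraph describes variable blocks of 2 to 6 at household level and states no stratification factors, so the design does not supply a covariate list either.

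**The concern.** A covariate improves an adjusted estimate to the extent that it predicts the outcome. The size of its difference between arms in one sample is a poor guide to that. A rule based on observed imbalance leaves the model unknown until the data are in. It may bring in variables with no prognostic value, and it may omit good predictors because they happen to be balanced. With no list and no threshold, several adjusted models would all satisfy the plan.

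The stigma analysis raises a related but separate question. A change score uses the baseline value with a fixed weight of one. Regressing the end-of-visit score on the baseline score estimates that weight, and is more precise whenever the correlation is below one. Stigma is the primary outcome but has no sample-size calculation of its own, so precision that costs nothing is worth taking.

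**Working it through.** **The plan's own figure.** Inputs from Sample Size (Section I.4): uptake 0.85 and 0.98, alpha 0.05 (taken as two-sided), power 90%, ICC 0.59, two contacts per household. The pooled two-proportion formula gives [1.96·√(2·0.915·0.085) + 1.2816·√(0.85·0.15 + 0.98·0.02)]² / 0.13² = 94.6 contacts per arm.
- Two contacts per household: the design effect is 1 + 0.59 = 1.59, and 94.6 × 1.59 / 2 = 75.2, so 76 households per arm and 152 in total.
- Three contacts per household: the design effect is 2.18, and 94.6 × 2.18 / 3 = 68.7, so 69 per arm and 138 in total.

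Both stated totals reproduce with no covariate adjustment in the calculation.

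**How often an imbalance rule fires by chance.** Suppose eight independent baseline variables are screened (the number is assumed). The chance that at least one looks unbalanced is 1 − 0.95⁸ = 34% at p<0.05 and 1 − 0.80⁸ = 83% at p<0.20.

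**What the rule gains.** An illustrative simulation used 76 households per arm, two contacts each, a continuous outcome, an assumed within-household correlation of 0.4, eight covariates of which one correlates 0.5 with the outcome, no treatment effect and 6,000 replicates.

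| Model | Mean model SE | SD of estimates | Type I error |
|---|---|---|---|
| Unadjusted | 0.136 | 0.136 | 5.2% |
| Covariates unbalanced at p<0.05 | 0.136 | 0.133 | 4.6% |
| Covariates unbalanced at p<0.20 | 0.134 | 0.127 | 4.0% |
| Prognostic covariate named in advance | 0.118 | 0.119 | 5.2% |

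The reported SE barely moves under imbalance selection. Taking the smallest p-value from the first three models gives 6.2% type I error. The cost is therefore mainly lost precision and an undefined model; error inflation is modest.

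**Stigma: change score against baseline adjustment.** Assume equal variance before and after, and the same correlation r between and within households. In units of the outcome variance, the change score has variance 2(1 − r) and the baseline-adjusted score 1 − r². Their ratio is (1 + r)/2, and the ICC cancels.

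| r (assumed) | Change, 2(1−r) | Adjusted, 1−r² | Ratio | SE reduction, 1−√ratio |
|---|---|---|---|---|
| 0.3 | 1.40 | 0.91 | 0.65 | 19% |
| 0.5 | 1.00 | 0.75 | 0.75 | 13% |
| 0.7 | 0.60 | 0.51 | 0.85 | 8% |
| 0.9 | 0.20 | 0.19 | 0.95 | 3% |

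Power is illustrative only. Take a 0.2 SD effect, borrow the uptake ICC of 0.59, and use an effective size of 152/1.59 = 95.6 contacts per arm. Power = Φ(0.2/SE − 1.96), with SE = √(4(1−r)/95.6) for change and √(2(1−r²)/95.6) for the adjusted score. It rises from 28% to 36% at r = 0.5 and from 43% to 49% at r = 0.7.

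**Uptake: room for covariates.** With 304 contacts, there are 152 per arm. Expected non-testers are 0.15 × 152 = 22.8 in control and 0.02 × 152 = 3.0 in intervention, about 26 in all and clustered. Three single-term covariates plus treatment make four coefficients, or 26/4 = 6.5 non-testers per coefficient. The list cannot be long.

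**The case against.** The strongest reply is that little hangs on this sentence. The adjusted model is secondary, the plan promises only to consider it, and the study is a pilot. That stands. A reader might infer that the trial's main result is data-driven, but the documents do not support this: neither the intention-to-treat uptake comparison nor the stigma-change analysis is selected by imbalance.

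A reader might also infer that the baseline stigma information is discarded unless it happens to look unbalanced. It is not, because the outcome is change. Set against an analysis of the end-of-visit score alone, baseline adjustment would save 13% to 29% of the SE at r = 0.5 to 0.7 (1 − √(1 − r²)), but the plan never proposes that analysis. Only the gain over the change score counts. The multilevel models are also described too briefly to exclude a baseline term.

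It is tempting to call every imbalance chance because the trial is randomised. That does not hold for contacts here. Households are allocated when the index patient is enrolled. Contacts are listed and consented later, at the home visit, by teams fixed to one arm. Differential recruitment is possible, so examining contact-level imbalance is reasonable. It does not follow that imbalance should choose the model.

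Finally, the baseline score is taken after allocation and possibly after the arm-specific introductory script described under Procedures for all households, so it may already reflect the arm. This is a real limitation, but the change score relies on the same measurement and shares it.

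**Conclusion.** The point holds, at moderate weight. The optional adjusted model is defined by a rule that makes its result depend on the data and selects covariates on the wrong criterion. The sentence follows the uptake analysis. For uptake the case rests on fixing the model in advance: the precision gain is unknown and may be small with about 26 non-testers.

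For stigma, the avoidable loss is the gap between a change score and baseline adjustment, about 13% of the SE at r = 0.5 and 8% at r = 0.7, shrinking as r rises. The correlation is assumed. The documents give no ICC, SD or target effect for stigma, so the power figures are illustrations and do not show that the stigma comparison is under-powered.

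**What to change.** In Section I.13, replace selection by imbalance with covariates named before outcomes are seen by arm:
- **Stigma models:** end-of-visit score as the outcome, adjusted for the baseline score on the same scale, age, gender and prior HIV testing, with household clustering as planned.
- **Secondary adjusted uptake model:** prior HIV testing, age and gender only, one term each. The unadjusted intention-to-treat comparison stays the main uptake analysis.
- **Imbalance:** tabulate contact characteristics by arm descriptively, because contacts are enrolled after allocation, and do not use the table to choose covariates.
- **Limitation:** state that baseline stigma is measured after allocation and possibly after an arm-specific introduction, and that this applies equally to the change score.

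The Aim 2 Analysis paragraph of Section I.4 should carry the same wording. The cost is an edit to the analysis text. All the variables are already collected, and no visits, participants or procedures change.
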